We will use descriptive statistics to describe clinical and demographic characteristics by treatment group and time. To evaluate differences in insomnia severity, sleep characteristics (Aim 1a), symptoms, PVT (Aim 1b) and functional performance (Aim 2) over the four time points (baseline, 3, 6, and 12 months), we will use GLMM with a repeated measures statement to examine group, time, and group by time effects. Nonlinear time effect will be controlled by transforming a continuous time variable with cube root form, which allows to estimate relatively rapid change in early at post-intervention than the follow-ups. We will choose the best covariance structure (compound symmetry vs. unstructured vs. moving average) by comparing the Akaike Information Criterion (AIC) and Bayesian Information Criterion (BIC). In multivariate models, adjusted intervention effects will be estimated by including covariates that might differ by group assignment (e.g., LVEF, comorbidity, age, SA with CPAP use). We will assess multi-collinearity among covariates with the variance inflation factor (VIF) and eliminate variables with high VIF (> 10) if the intervention effect is not modified after elimination. We will identify influential outliers with DFFITS, DFBETAS, and Cook’s distance. If there are non-normally distributed residuals, the outcome variable will be transformed to ordinal form or fitted with more flexible distributions (e.g., Gamma, Poisson). We will use GEE with a robust working correlation structure to address within-subjects correlations for changes in outcomes with clinical cutoffs (i.e., $ISI \geq$, $ESS \geq 10$, $PSQI \geq 5$, $SMW \geq 1000$) over time. To avoid the inflation of type 1 error, False Discovery Rate (FDR) will be calculated for post-intervention effects on 13 outcome variables. .

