Sample Size. We performed power analyses to detect the effects of CBT-I on primary outcomes [insomnia severity, sleep quality (PSQI), self-reported (PSQI) and actigraph sleep efficiency (SE), and fatigue] with pilot data in which we randomized HF patients to CBT-I (HS) or attention control (HH). We calculated powers to detect differences in changes in outcomes from BL between the two groups to post-intervention (2 wks/T1) with 5% type I error.¹¹⁷ We also calculated powers with scenarios of high within-subjects correlations (Rho=0.6, 0.7, 0.8) for repeated measures during F/U (2 wks, 6, , 12 months) by assuming consistent effect sizes over time¹¹⁸ (Table 3). A sample of 100 independent participants per group will yield $> 90\%$ power to detect CBT-I effects on insomnia severity (ES=0.65), fatigue (ES=0.64), and PSQI sleep quality (ES=0.46) and power of 76.6% for PSQI SE (ES=0.38), but a power of 99.9% for actigraph-measured SE (ES=0.70). In scenarios based on within-subjects correlations of outcomes, we anticipate $> 95\%$ power for most outcomes and $> 80\%$ power for self-reported SE. Inclusion of 200 subjects (100/group) will permit sufficient power to detect the association between improved insomnia severity and symptoms [fatigue ($>99.9\%$, $r = 0.526$), depression (99.16%, $r = 0.299$), anxiety ($> 99.9\%$, $r = 0.510$), and pain (92.7%, $r = -0.238$)]. There will be 92.6% power to detect risk of hospitalization in participants with insomnia remission (9%), compared to no remission (27.8%). We will randomly assign 200 participants in 25-33 clusters of 6-8. Because we do not expect dependency among participants in the same clusters, we will not increase the sample for random cluster assignment.

We computed the power for estimating cost-effectiveness with Willan¹¹⁹ and Glick's¹²⁰ methods, based on an assumed alpha level of 0.05, expected cost difference of \$500, standard deviation for costs of \$2,000, expected correlation between costs and QALYs of -0.1, and willingness-to-pay of \$50,000 per QALY. The expected difference in QALYs, based on the pilot study, is estimated to be -0.33. Together, these values suggest that the sample of 100 subjects/group yields 89.7% power for detecting cost-effectiveness of CBT-I.

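### The mixed-model covariance is chosen from the data by AIC and BIC with no rule for when they differ; if the correlation departs mildly from compound symmetry, following BIC can put a 12-month change test at about 6–8% instead of 5%

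*Combined protocol and SAP*

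**What the plan says.** The same text appears in the protocol (Data Analysis, under Data Management and Statistical Analysis Plan) and in the Data Analysis section of the Statistical Analysis Plan. Continuous outcomes are compared "over the four time points (baseline, 3, 6, and 12 months") with a mixed model containing group, time and their interaction. On time, the plan adds: "Nonlinear time effect will be controlled by transforming a continuous time variable with cube root form". On covariance, the analysts will "choose the best covariance structure (compound symmetry vs. unstructured vs. moving average) by comparing the Akaike Information Criterion (AIC) and Bayesian Information Criterion".

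Robust handling is stated only for the dichotomised outcomes: "We will use GEE with a robust working correlation structure to address within-subjects correlations for changes in outcomes with clinical cutoffs". Nothing comparable is stated for the mixed model.

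The Sample Size section is the only place that describes correlation over visits. It uses "scenarios of high within-subjects correlations (Rho=0.6, 0.7, 0.8) for repeated measures during F/U", one value per scenario. It gives no correlation between baseline and follow-up and no pattern by time gap.

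**The concern.** AIC and BIC penalise parameters differently, so naming both without a tie-break leaves the rule incomplete. Where they differ, two defensible analyses with different standard errors remain, and the choice is made with the data in hand.

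The choice affects validity. Compound symmetry imposes one variance and one correlation on visits at 0, 3, 6 and 12 months. If the true baseline-to-12-month correlation is below the average of the six pairwise correlations, compound symmetry understates the standard error of change to 12 months. That is the comparison a reader would use to judge whether the effect is sustained, and the rule governs every primary outcome analysed by the mixed model. The planned false discovery rate step does not help, because it takes each p-value as valid.

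**Working it through.** **Inputs.** From Sample Size: "A sample of 100 independent participants per group will yield" the stated powers, "with 5% type I error", and Rho of 0.6, 0.7 or 0.8. From Data Analysis: four visits. From Table 2: pilot means, SDs and effect sizes. All other correlation patterns below are assumptions.

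**The plan's own figures.** Two-sided power is Φ(ES·√(100/2) − 1.96). For PSQI sleep quality, 0.46 × 7.071 = 3.253, giving Φ(1.293) = 90.2%, as in Table 3. For repeated measures, divide ES by √((1+(m−1)Rho)/m). With Rho 0.6 and m = 4 this is √0.70 = 0.837, so 3.253/0.837 = 3.888 and Φ(1.928) = 97.3%, again as in Table 3. (The plan lists three follow-ups; m = 3 changes the powers by less than 2 points.) The power calculation thus assumes an exchangeable correlation.

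**How far apart the criteria are.** Unstructured has 4·5/2 = 10 parameters and compound symmetry has 2, a difference of 8. AIC moves to unstructured when the likelihood ratio exceeds 2·8 = 16. BIC needs 8·ln(200) = 42.4, or 8·ln(800) = 53.5 if observations rather than people are counted.

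**Error if compound symmetry is kept.** With equal variances, the fitted variance of change is proportional to 1 − r̄, where r̄ is the mean of the six correlations; the true value is proportional to 1 − r(0,12). The actual error is about 2Φ(−1.96·√[(1 − r̄)/(1 − r(0,12))]).

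- Lag correlations 0.70/0.65/0.60: r̄ = (3·0.70 + 2·0.65 + 0.60)/6 = 0.667; ratio 0.333/0.40 = 0.833; √ = 0.913; error 2Φ(−1.789) = 7.4%.
- Baseline–follow-up 0.40, among follow-ups 0.60: r̄ = 0.50; ratio 0.50/0.60 = 0.833; error 7.4%.

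**Simulation.** No effect, 100 per arm, complete normal data, arm-by-visit means, REML, model-based standard errors, 6,000 runs per pattern. Monte Carlo standard error at 5% is √(0.05·0.95/6000) = 0.3 point. Candidates here are compound symmetry and unstructured.

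| Assumed pattern | Criteria disagree | Error with compound symmetry kept |
|---|---|---|
| Exchangeable 0.6–0.8 | 4–5% | 5.0–5.1% |
| Lags 0.60/0.55/0.50 | 35% | 6.8% |
| Lags 0.70/0.65/0.60 | 58% | 7.4% |
| Lags 0.75/0.70/0.65 | 73% | 7.8% |
| Lags 0.80/0.75/0.70 | 81% | 8.5% |
| Baseline–follow-up 0.55, follow-up 0.65 | 54% | 6.5% |
| Baseline–follow-up 0.60, follow-up 0.70 | 66% | 6.7% |
| Lags 0.70/0.60/0.50 | 54% | 9.6% |
| Lags 0.80/0.70/0.60 | 3% | rarely kept |
| AR(1) 0.7 | about 0% | both choose unstructured |
| Exchangeable 0.7, pilot ISI SDs | 69–80% (ISI or fatigue) | 4.1% |
| Exchangeable 0.7, pilot fatigue SDs | as above | 6.1% |

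Following BIC throughout, whichever structure it picks, gave 6.2% (baseline–follow-up 0.55, follow-up 0.70), 6.9% (0.40 and 0.60) and 8.2% (lags 0.65/0.55/0.45). Unstructured gave 4.6%, 5.2% and 5.2% on the same patterns. Following AIC gave about 4.6–6.2% in the lag-decay cases.

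**The moving-average candidate.** Read as order 1, it is never chosen and changes nothing. Read as a full banded Toeplitz matrix, error under BIC falls to 6.0% at 0.70/0.65/0.60, 5.8% at 0.75/0.70/0.65 and 5.3% at 0.70/0.62/0.54. In the baseline–follow-up 0.40 pattern it helps little (6.8%).

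**A hint from the pilot.** Assume the Table 2 effect sizes are the difference in change divided by the SD of change. For ISI at T1 the changes are −7.62 and −3.68, so the SD of change is 3.94/0.65 = 6.06. With pooled SDs of 4.62 and 5.25, r = (4.62² + 5.25² − 6.06²)/(2·4.62·5.25) = 0.25. The same steps give 0.48 for ISI at T2, 0.39 for PSQI and 0.43 for PSQI sleep efficiency, but 0.61 and 0.71 for fatigue.

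**The case against.** The strongest reply is that nothing in the documents says compound symmetry is wrong here. The only stated correlation is a single Rho per scenario, and under that assumption the criteria almost always agree and the test holds its level. A reader might infer that AIC and BIC will usually disagree in this trial, and that the 12-month test will therefore run at 7–8%. The documents do not support that: they give no decay with time, and under stronger decay both criteria choose unstructured. The direction is not fixed either. With the pilot ISI SDs and an exchangeable 0.7, compound symmetry is slightly conservative, and the plain arm difference at 12 months stays near 5% when SDs are equal over time.

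It would also be too strong to call the choice after the fact. Candidates and criteria are named in advance; the rule is data-driven and incomplete.

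Nor is the simulated contrast written in the plan, which specifies cube-root time by group. It is a natural reading of the hypothesis of effects sustained at 6 and 12 months. The cube-root slope is affected too, at about 8.1–8.6% when compound symmetry is kept in comparable patterns.

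These points stand, and they make the size conditional. They do not supply the missing tie-break. The exchangeable Rho also covers follow-up only. The pilot back-calculation suggests lower baseline-to-follow-up correlations for three of the five primary outcomes, although it rests on 48 completers and an assumed definition of effect size.

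**Conclusion.** The selection rule is incomplete, and the gap can affect validity. How much depends on assumptions:

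- **Exchangeable correlation:** disagreement in about 4–5% of trials; error 5%.
- **Mild decay, or somewhat lower baseline–follow-up correlation:** disagreement in about 35–80%; a BIC-governed test of baseline-to-12-month change at about 6–8%.
- **Compound symmetry kept, over the plausible patterns tried:** about 4–10%.
- **Stronger departures:** both criteria choose unstructured and the problem disappears.
- **Moving average read as full banded Toeplitz:** about 5–6% under BIC in the lag-decay cases.

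The figures also assume model-based standard errors, complete data and normal outcomes; attrition was not modelled. This is a worthwhile, inexpensive correction rather than a demonstrated failure of the primary analysis.

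**What to change.** In both Data Analysis sections, replace the AIC/BIC sentence with wording such as: *Continuous outcomes analysed by the linear mixed model will use an unstructured covariance matrix with Kenward-Roger degrees of freedom. If this model does not converge, compound symmetry with sandwich standard errors will be used.* Drop the moving-average option. A Toeplitz fallback is best avoided as well, because it is also indexed by visit order although the visits are unequally spaced.

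Four visits and about 200 people readily support 10 covariance parameters. The cost is one sentence in two places and a negligible loss of precision if compound symmetry is true.

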$$\text{ICER} = \frac{C_{\text{CBT-I}} - C_{\text{HH}}}{E_{\text{CBT-I}} - E_{\text{HH}}}$$

($C_{\text{CBT-I}}$: expected cost of the intervention; C_{HH} : expected costs for the HH group; $E_{\text{CBT-I}}$: effectiveness of the intervention, measured as QALYs; E_{HH} : effectiveness in the HH group). ICER represents the incremental cost to gain an additional QALY with CBT-I. We will discount costs over the 3 years of data collection and estimate uncertainty around the ICER by bootstrapping, yielding a 95% confidence ellipse around the ICER. In the usual cost-effectiveness framework, a willingness to pay threshold is used to determine cost-effectiveness of a treatment. However, in a stochastic cost-effectiveness framework, we can estimate the probability that CBT-I is cost-effective over a wide range of willingness to pay thresholds with the cost-effectiveness acceptability curve (CEAC). We will perform sensitivity analyses for costs, life expectancy, and utility.

We will use survival analysis for exploratory aim 1 and compare time to EFS between CBT-I and the attention control condition with a competing risk approach.¹⁹⁷ This approach accounts for the relationship of the occurrence of one event with others. Participants who do not experience events during f/u will be right-censored. As a secondary analysis, we will examine time to specific events (e.g., hospitalization, death). We will adjust the survival model by including baseline Seattle Heart Failure score,¹⁸⁶ depression, LVEF, adherence,³⁶ and self-care/self-care management,⁷⁷ as they predicted EFS.
